8.4.2.2 Secondary Efficacy Analysis

Each secondary efficacy endpoint will be summarized by treatment group at each time point, as appropriate.

Following secondary endpoints will be analyzed:

1. Changes from baseline to Week 12 and Week 24 in liver enzymes/LFTs: Alanine aminotransferase (ALT), aspartate aminotransferase (AST), alkaline phosphatase (ALP), Gamma-glutamyl transferase (GGT), serum protein, albumin and total bilirubin.
2. Changes from baseline to Week 12 and Week 24 in insulin resistance as measured by HOMA.

Approved by: [name]	Protocol No. SARO.17.009 Version No.: 5.0
------------------------------------	--

 Zydus Discovery DMCC	CLINICAL TRIAL PROTOCOL Saroglitazar Magnesium – Phase 2A SARO.17.009	Confidential Page 63 of 82
--	---	-------------------------------

3. Changes from baseline to Week 24 in markers of liver injury and fibrosis including CK-18, hs-CRP, TNF α , and liver stiffness measured by transient elastography/FibroScan[®].
4. Changes from baseline to Week 24 in controlled attenuation parameter measured by transient elastography/ FibroScan[®].
5. Changes from baseline to Week 12 and Week 24 in body weight, BMI and in waistcircumference.
6. Changes from baseline to Week 24 in MRI-derived measures of total liver fat index and total liver volume.
7. Changes from baseline to Week 12 and Week 24 in lipid and lipoprotein levels: TG, TC, HDL, LDL, sdLDL, VLDL, apolipoprotein A and apolipoprotein B.
8. Changes from baseline to Week 12 and Week 24 in SHBG level.
9. Changes from baseline to Week 12 and Week 24 in ovarian function (Total testosterone, 17-hydroxyprogesterone, free testosterone, luteinizing hormone, follicle-stimulating hormone, LH-to-FSH ratio and estradiol).
10. Changes from baseline to Week 12 and Week 24 in free androgen index.
11. Pharmacokinetics of Saroglitazar following first dose and last dose.

The change from baseline will be determined as:

Change = (Post-baseline – Baseline)

Percent change will be calculated for all parameters except those measured in ratio or percent.

Percent Change = $((\text{Post-baseline} - \text{Baseline}) / \text{Baseline}) * 100$

Treatment effects will be estimated using the least-square mean, standard error and 95% confidence interval from ANCOVA model with treatment as factor and baseline value as covariate. Treatment groups, Saroglitazar Magnesium 4 mg Tablets and placebo, will be compared using the difference in least-square means and p-values from the ANCOVA model.

Descriptive statistics will be provided for each Pharmacokinetic parameter as detailed in Section 7.3.

Above analysis will also be supported by simple summaries at each visit. Unless otherwise stated, all the continuous variables will be represented by n, mean, standard deviation, minimum, median and maximum. All the categorical variables will be presented as frequencies and percentages.

Approved by: [name]	Protocol No. SARO.17.009 Version No.: 5.0
------------------------------------	--

 Zydus Discovery DMCC	CLINICAL TRIAL PROTOCOL Saroglitazar Magnesium – Phase 2A SARO.17.009	Confidential Page 64 of 82
---	---	-------------------------------

8.4.3 Safety Analysis

All safety analysis will be carried out on the safety population. The frequency tabulations of abnormal clinical laboratory values for the parameter will be presented for each treatment group by visit. Summary statistics for clinical laboratory parameters, ECGs, physical examination and vital signs will be presented for each treatment by visit.

All AEs observed during the study period will be listed. Incidence of all AEs reported during the study will be summarized using the MedDRA (version 19 or higher) by treatment group, frequency, severity, seriousness, relationship to study drug and expectedness per System Organ Class and Preferred Term.

8.4.4 Baseline Characteristics

Demographic and baseline characteristics will be summarized by treatment and population set. Subject disposition and reason for withdrawal will be summarized and presented. Unless otherwise stated, all the continuous variables will be represented by n, mean, standard deviation, minimum, median and maximum. All the categorical variables will be presented as frequencies and percentages.

8.4.5 Interim Analysis

No interim analysis is planned for the study.

8.5 HANDLING OF MISSING DATA

Clarifications, wherever possible, will be obtained from the respective Investigator for any missing data or for any illegible entry, unused or unauthenticated data and this will be recorded in the data handling report before the final database lock.

Subjects who are discontinued from the study will be excluded from PP population. Any randomized subject who discontinued the study for any reason but have at least 1 post-baseline efficacy data will be included in the mITT population. Last Observation Carried Forward method will be used as an imputation method for the efficacy variables for mITT population.

8.6 DETERMINATION OF SAMPLE SIZE

The primary efficacy endpoint of this study is the change from baseline in hepatic fat content at Week 24 as measured by MRI-PDFF. There is no data available on the change from baseline in hepatic fat content measured by MRI-PDFF.

Approved by: [name]	Protocol No. SARO.17.009 Version No.: 5.0
------------------------------------	--

 Zydus Discovery DMCC	CLINICAL TRIAL PROTOCOL Saroglitazar Magnesium – Phase 2A SARO.17.009	Confidential Page 65 of 82
--	---	-------------------------------

A sample size of 74 completed subjects (37 subjects in each treatment arm) will provide 80% power to detect a 4% treatment difference in change from baseline in hepatic fat content at Week 24 between Saroglitazar 4 mg and Placebo using a two-sided 5% level of significance based on a two-sample t-test, assuming change from baseline in hepatic fat content of 9% at Week 24 in Saroglitazar 4 mg treatment arm with a common standard deviation of 0.6.

Assuming a 20% dropout rate at week 24, approximately 90 subjects will be randomized in a 1:1 ratio to receive either Saroglitazar 4 mg (45 subjects) or placebo (45 subjects). Additional subjects may be enrolled if the dropout rate is more than 20%. The sample size estimation was performed using PASS 14 software.

A total of 12 subjects, 6 subjects in each treatment arm will be included in the pharmacokinetic assessment.

Additional patients may be enrolled into the study to ensure the pharmacokinetic assessment is performed on at least 6 completed patients in each treatment arm.

8.7 RANDOMIZATION

Subjects will be randomly assigned in a 1:1 treatment allocation ratio to Saroglitazar Magnesium 4 mg Tablets and placebo, respectively. The randomization schedule will be generated to ensure the treatment balance by using SAS® software (Version: 9.4 or higher; SAS Institute Inc., USA).

Approved by: [name]	Protocol No. SARO.17.009 Version No.: 5.0
------------------------------------	--

 Zydus Discovery DMCC	CLINICAL TRIAL PROTOCOL Saroglitazar Magnesium – Phase 2A SARO.17.009	Confidential Page 66 of 82
---	---	-------------------------------

9 ADMINISTRATIVE MATTERS

The trial will be carried out in compliance with the protocol, in accordance with the International Council for Harmonisation (ICH) guideline for GCP and in accordance with applicable regulatory requirements.

9.1 ETHICS

9.1.1 Institutional/independent Committee Review and Communications

The trial will not be initiated before the protocol and informed consent and subject information form have been reviewed and have received approval / favorable opinion from the IEC/IRB. Should a protocol amendment be made that requires IEC/IRB approval, the changes in the protocol will not be instituted until the amendment and revised informed consent (if appropriate) has been reviewed and received approval / favorable opinion from the IEC/IRB. A protocol amendment intended to eliminate an apparent immediate hazard to subjects may be implemented immediately provided that the appropriate regulatory authorities and IEC/IRB are notified as soon as possible and an approval is requested. Protocol amendments only for logistical or administrative changes may be implemented immediately; however, both the IRB/IEC and the Regulatory Authority will be notified as soon as possible. The constitution of the IEC/IRB must comply with the requirements of the US Code of Federal Regulations. A list of the IEC/IRB members, with names and qualifications, will be requested. If such a list is unavailable, the Investigator must provide the name and address of the central IEC/IRB along with a statement from the IEC/IRB that it is organised according to GCP and the applicable laws and regulations. The IEC/IRB must also perform all duties outlined by the requirements of the regulatory agencies.

9.1.2 Informed Consent and Subject Information

Prior to subject participation in the trial, written informed consent will be obtained from each subject (or the subject's legally authorized representative) according to the regulatory and legal requirements of the participating country. Each signature must be dated by each signatory and the informed consent and any additional subject information form retained by the Investigator as part of the study records. A signed copy of the IEC/IRB approved informed consent and any additional subject information must be given to each subject or the subject's legally authorised representative.

The subject must be informed that her medical records may be examined by authorised monitors or Clinical Quality Assurance auditors appointed by the Sponsor, by appropriate IEC/IRB members and by inspectors from regulatory authorities.

Approved by: [name]	Protocol No. SARO.17.009 Version No.: 5.0
------------------------------------	--

 Zydus Discovery DMCC	CLINICAL TRIAL PROTOCOL Saroglitazar Magnesium – Phase 2A SARO.17.009	Confidential Page 67 of 82
---	---	-------------------------------

Should a protocol amendment be made, the subject consent form and subject information form may need to be revised to reflect the changes to the protocol. It is the responsibility of the Investigator to ensure that an amended consent form is reviewed and received approval from the IEC/IRB, and to further ensure that it is signed by all subjects subsequently entered in the trial and those currently in the trial, if affected by the amendment.

9.2 RECORDS

9.2.1 Drug Accountability

The dispensing of study drug to the subject, and the return of the study drug from the subject, must be documented on drug accountability form. Subject or their legally authorized representative, must be instructed to return all the original containers, where empty or containing study drug. The subjects must return unused study drug to the site.

Receipt and dispensing of study drug must be recorded by an authorized person at the study site. The PI will maintain an accurate record of the receipt of the study drug as shipped by the Sponsor, including the date received. Study drug supply management will be processed and maintained on drug accountability forms, which will be monitored and reconciled by the study monitor assigned to the site. This inventory record must be available for inspection at any time. Copies of this record will be provided to the Sponsor at the conclusion of the study. The PI will not be allowed to store study drug at any site other than those listed on Form FDA 1572 or Investigator's Agreement or to dispense the study drug from sites not listed on this form. The PI will also agree that study drug will be dispensed by the PI or Sub-investigator named on Form FDA 1572 or Investigator's Agreement, or their qualified designees. The PI, Sub-investigators and qualified designees also agree that study drug will be dispensed only to study patients who have provided written informed consent and have met all entry criteria. Study drug may not be used for any purpose other than that stated in the protocol.

After the study has been completed, the PI must account for all study drug used, unused and partially used. All study drugs will be adequately destroyed at the site (per site's SOPs) or returned to the Sponsor (or designee). No study drug will be destroyed or returned until drug accountability has been performed by the study monitor.

9.2.2 Emergency code break (Unblinding)

An emergency code break will be available to the investigator and / or pharmacist. This code break must only be opened in emergency situations when the identity of the study drug must be known by the investigator in order to provide appropriate medical treatment. If the code break for a subject is opened, Sponsor must be informed immediately. The reason for opening the code break must be documented along with the date and the initials of the person who broke the code.

Approved by: [name]	Protocol No. SARO.17.009 Version No.: 5.0
------------------------------------	--

 Zydus Discovery DMCC	CLINICAL TRIAL PROTOCOL Saroglitazar Magnesium – Phase 2A SARO.17.009	Confidential Page 68 of 82
--	---	-------------------------------

Subjects whose treatment assignment becomes unblinded inadvertently, need not require to complete the scheduled evaluations and patient will be withdrawn from the trial from that visit.

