4.4 PATIENT WITHDRAWAL

Patients may withdraw from the entire study at any time without penalty and for any reason without prejudice to her future medical care. Although a patient is not obliged to give her reason for withdrawing prematurely, the PI will make a reasonable effort to obtain the reason while fully respecting the patient's rights. If there is a medical reason for withdrawal, the patient will remain under the supervision of the PI for follow-up of AE(s) as detailed in Section 9.4.1.6. Every effort will be made to continue clinical and/or laboratory follow-up, as appropriate, in patients who wish to withdraw from the study drug (Investigational product or placebo) and reasonable efforts will be made to contact a patient who fails to attend any follow-up appointments, in order to ensure that she is in satisfactory health. A patient's withdrawal of consent and agreement to undergo a final examination will be documented on the electronic case report form (e-CRF).

As far as possible, all assessments scheduled for end-of-treatment must be performed on all patients who receive the study drug but do not complete the study according to protocol. In addition, if patient withdraws from the study, any data collected during the period of time will be maintained as part of the study data.

 Zydus Discovery DMCC	CLINICAL TRIAL PROTOCOL Saroglitazar Magnesium – Phase 2A SARO.17.009	Confidential Page 43 of 82
---	---	-------------------------------

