4.4.1 Discontinuation of Patients from the Study or Study Drug

A patient may be discontinued from the study for any of the following reasons:

- Noncompliance to the protocol requirements.
- Occurrence of a serious or intolerable AE and based upon the Investigators' clinical judgment.
- The Sponsor or PI terminates the study (Section 4.6).
- Either the PI or the Sponsor decides that discontinuing the study or discontinuing the patient is in the patient's best interest.
- For reasons related to safety as specified in Section 4.5.
- The patient is lost to follow-up.
- A patient may also be discontinued from study drug/study by the Sponsor, Regulatory Authorities or Institutional Review Board (IRB) or Independent Ethics Committee (IEC).
- If the patient becomes pregnant.

A study completion eCRF, which includes the reason for discontinuation, must be completed for all patients who are discontinued from the study. If the patient is discontinued prematurely, the study completion eCRF should clearly indicate the reason for discontinuation. If the patient discontinues due to an AE, an AE eCRF must be completed. The AE must be followed by medical attention to satisfactory resolution and all study data related to the patient will be reported.

Every effort will be made to continue clinical and laboratory follow-up, as appropriate, in patients who are withdrawn or in whom the study drug is stopped by the PI or per individual stopping rules (Section 4.5).

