Visit 2 (Day -14 to -7): Liver function tests (AST, ALT, ALP, GGT, total protein, albumin, total bilirubin (with conjugated bilirubin) will be re-measured approximately 2 weeks from Day - 28 to determine eligibility.

Alanine transaminase ≥ 38 U/L at Visit 1. Visit 2 ALT must not increase $>30\%$ from Visit 1.

Randomization and Treatment Phase

Visit 3 to Visit 8: The randomization and treatment phase will include 6 outpatient visits (Visit 3 to Visit 8) over a period of 24 weeks including the randomization visit. All the eligible subjects will be randomly assigned into either of the two treatments arms: Saroglitazar Magnesium 4 mg Tablets and matching placebo tablets in a 1:1 ratio. Efficacy assessments will be conducted at 12 (hormonal profile, lipid and lipoprotein profiles, ovarian function and liver enzymes/LFTs) and 24 weeks visits (liver fat content by MRI-PDFF, hormonal profile, lipid and lipoprotein profiles, MRI-derived total liver fat index and total liver volume, homeostasis model assessment [insulin resistance (HOMA-IR)], liver stiffness by transient elastography/FibroScan®, controlled attenuation parameter, ovarian function and liver enzymes/LFTs). In addition, subjects will be monitored during the study and at every visit for development of any adverse events including drug induced liver injury. In addition to physical examination, laboratory data and ECGs done during the study period will be monitored to detect any treatment emergent adverse events.

Visit 3 (Week 1, Day 1): Patients will be randomly assigned to receive Saroglitazar Magnesium 4 mg Tablets or placebo orally once-daily, starting on Day 1 of a 24-week outpatient treatment period.

Visits 4, 5, 6, 7 and 8: Patients will visit the study site at Week 2 (Visit 4), Week 8 (Visit 5) Week 12 (Visit 6), Week 16 (Visit 7) and Week 24 (Visit 8) for clinical assessment, dispensation and reconciliation of study drug, measurements of efficacy endpoints and assessment of AEs.

Detailed efficacy and safety assessments are provided in Table 1 (Time and Events Schedule).

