7.2 Study Methodology

Pre-Screening:

An informed consent will be obtained from the potential participants before any pre-screening evaluations. The evaluation of the ALT levels during the pre-screening will be done at the local laboratory, whereas the laboratory evaluations during the screening and the treatment phase will be done at the central laboratory.

Screening Phase:

The screening phase will consist of 28 days. Unless otherwise specified, screening procedures may be completed at any time during the screening phase. Before each participant is enrolled to the study, informed consent will be obtained from the participant (or her legally authorized representative) according to the regulatory and legal requirements of the participating country. Participant eligibility criteria for participation in the study will be assessed. Participants will undergo a serum pregnancy test. During this phase participant will be seen by the investigator or designated study personnel and an AUDIT questionnaire will be administered.

Randomization and Treatment Phase:

The randomization and treatment phase will include 6 outpatient visits (Visit 3 to Visit 8) over a period of 24 weeks including the randomization visit. All the eligible participants will be randomly assigned into either of the two treatment arms: Saroglitazar Magnesium 4 mg tablets and matching placebo tablets in a 1:1 ratio. Efficacy assessments will be conducted at Visit 6 Week 12 and Visit 8 Week 24 visits. In addition,

Document Title:	Statistical Analysis Plan		
Version Number:	Final 1.0	Date:	18Oct2024
Protocol Number:	SARO.17.009	Sponsor Name:	Zydus Therapeutics INC

participants will be monitored during the study and at every visit for development of any adverse events including drug induced liver injury. In addition to physical examination, laboratory data and ECGs done during the study period will be monitored to detect any treatment emergent adverse events.

Safety Follow-up Visit:

A final post-treatment visit will occur 6 weeks (± 3 days) [i.e. Visit 9 Week 30] after the end-of-treatment visit (i.e. Visit 8 Week 24) for safety monitoring. A telephonic follow-up visit will be performed to assess any AE or SAE after the end-of-treatment visit for safety monitoring. As far as possible, all assessments scheduled for end-of-treatment must be performed on all participants who receive the study drug but do not complete the study according to protocol.

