7.5 Blinding and Unblinding

The study will be performed in a double-blind manner. All study drug will be supplied in identical packages and study drug kits. The study drug tablets will be similar in color, smell, taste, and appearance, thereby maintaining double-blind conditions.

The study blind should not be broken except in a medical emergency where knowledge of the study drug received would affect the treatment of the emergency.

The blind must only be broken following a discussion on a case-by-case basis, at the discretion of the Sponsor/Medical Expert. If an emergency unblinding becomes necessary, the PI should notify the Sponsor/Medical Expert, if possible, before unblinding. If it is determined that unblinding is necessary, a scratch card will be decoded to reveal the treatment received by the participant. All cases resulting in an unblinding event will be documented and reported to the Medical Expert and the Sponsor. If the blind is

Document Title:	Statistical Analysis Plan		
Version Number:	Final 1.0	Date:	18Oct2024
Protocol Number:	SARO.17.009	Sponsor Name:	Zydus Therapeutics INC

broken, the date, time and reason must be recorded in the participant's eCRF/source document and any associated AE report completed.

The overall randomization code will be broken only for reporting purposes. This will occur once all final clinical data have been entered into the database, all data queries have been resolved, and the assignment of participants to the analysis sets has been completed.

Emergency code break (Unblinding):

An emergency code break will be available to the investigator and / or pharmacist. This code break must only be opened in emergency situations when the identity of the study drug must be known by the investigator in order to provide appropriate medical treatment. If the code break for a Participant is opened, Sponsor must be informed immediately. The reason for opening the code break must be documented along with the date and the initials of the person who broke the code. Participants whose treatment assignment becomes unblinded inadvertently, need not complete the scheduled evaluations and participant will be withdrawn from the trial from that visit.

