8.2 Analysis Populations

Participant evaluability and their impact on analysis populations will be determined prior to locking the database.

Analysis Population	Definition
Safety (SAF)	The Safety (SAF) analysis population will consist of all participants who: - Were Randomized, - Had administered at least one dose of investigational product.
Modified Intention to Treat (mITT)	Modified Intention to Treat analysis population will consist of all participants who: - Were randomized, - Had administered at least one dose of investigational product - Have at least 1 post-baseline efficacy data of primary outcome.
Per Protocol (PP)	The Per Protocol (PP) analysis population will consist of all participants who: - Were in mITT analysis population, - Completed the treatment phase (i.e., Had both baseline and end-of-treatment primary efficacy outcome & has taken $\geq 80\%$ and $\leq 120\%$ of the study drug) - Have no protocol deviations that could affect primary efficacy outcome.

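### Inadvertently unblinded participants are withdrawn and excused from evaluations, in conflict with the rule on end-of-treatment assessments; without her Week 24 MRI such a woman leaves both efficacy sets

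*Protocol*

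**What the plan says.** **The unblinding rule.** Under Protocol 9.2.2, subjects unblinded inadvertently "need not require to complete the scheduled evaluations and patient will be withdrawn from the trial from that visit". SAP 7.5 carries the same rule: they "need not complete the scheduled evaluations and participant will be withdrawn from the trial from that visit".

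**The non-completer rule.** Protocol 4.4 says that, so far as can be achieved, "all assessments scheduled for end-of-treatment must be performed on all patients who receive the study drug but do not complete the study". The protocol summary (Patient Withdrawal) and Protocol 7.2 repeat this. SAP 7.2 likewise says that "all assessments scheduled for end-of-treatment must be performed on all participants who receive the study drug" and do not complete. Protocol 4.4.1 adds: "Every effort will be made to continue clinical and laboratory follow-up, as appropriate, in patients who are withdrawn".

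**The primary measurement.** Protocol 7.2 places the post-baseline fat measurement at the "24 weeks visits (liver fat content by MRI-PDFF, hormonal profile" and other items follow in that list. MRI-PDFF is not among the Week 12 assessments.

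**The analysis sets.** Protocol 8.5: "Subjects who are discontinued from the study will be excluded from PP population". SAP 8.2 makes one condition of mITT: "Have at least 1 post-baseline efficacy data of primary outcome". SAP 8.4 limits multiple imputation of the primary variable to the mITT population.

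**The concern.** Knowing the assignment does not stop an outcome from being measured, and an MRI fat fraction is an imaging result rather than a self-report. A rule that excuses the participant from evaluations therefore creates missing primary data that could have been avoided. It also pulls against an instruction, given in several places, to collect exactly those data from dosed non-completers.

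The primary outcome has one scheduled post-baseline measurement. If it is skipped, no earlier MRI can stand in for it, and a randomised woman can leave the efficacy analyses for a reason unrelated to treatment response or to whether her outcome could be obtained.

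**Working it through.** The check is a comparison of text, followed by simple arithmetic for scale. The plan gives no figure of its own on this point.

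**1. Do the rules conflict?**

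| Source | Who is covered | Instruction | Exception for unblinding |
|---|---|---|---|
| Protocol 9.2.2, SAP 7.5 | Inadvertently unblinded | Withdrawn; evaluations not required | n/a |
| Protocol summary, 4.4, 7.2; SAP 7.2 | Dosed, did not complete | End-of-treatment assessments required, where feasible | None |
| Protocol 4.4.1 | Withdrawn, or drug stopped by the investigator or a stopping rule | Continue clinical and laboratory follow-up as appropriate | None |

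A woman who has taken drug and is withdrawn under 9.2.2 belongs to all three rows. The first row releases her from evaluations that the other two expect. Nothing says which takes precedence. The reasons for discontinuation in Protocol 4.4.1 do not name unblinding, nor do the intercurrent events in SAP 9.7.1.2.

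**2. What happens if she has no post-baseline MRI?**

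- *PP (primary analysis).* She is out: she was discontinued (Protocol 8.5), and she lacks the end-of-treatment primary outcome (SAP 8.2).
- *mITT as defined in the SAP (supportive).* She is out: the set requires a post-baseline value of the primary outcome.
- *Imputation.* It operates within mITT (SAP 8.4), so it cannot restore someone who is not a member.
- *Secondary endpoints.* SAP 9.7.2.2 uses the same two sets, so any Week 12 laboratory data she already gave also drop out of the efficacy comparisons.
- *Protocol definition of mITT.* Protocol 8.4.1.2 accepts any post-baseline efficacy data, which is wider. SAP sections 5 and 10 say that the SAP prevails, and carrying forward would in any case find no earlier post-baseline MRI.

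**3. Scale.** The frequency of inadvertent unblinding is not stated. The weight of a single case can be shown:

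- Recruitment closed at 60 (SAP 7.3, 8.5), allocation 1:1: 60 / 2 = 30 per arm; 1/30 = 3.3% of an arm as randomised.
- Assuming the planned 20% dropout: 30 × 0.80 = 24 per arm; 1/24 = 4.2% of an arm's completers.

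The second figure needs care. The 20% allowance may already include withdrawals of this kind, so taking one more from 24 could count the loss twice. Both figures are per case and are not estimates of the total loss.

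**The case against.** The strongest reply is that the passages can be read together. The unblinding rule is permissive: it excuses evaluations but does not forbid them. The non-completer rule is itself best-efforts. On this reading the woman is withdrawn, becomes a dosed non-completer, and the end-of-treatment assessments are then sought. This stands in part. A reader might infer that the Week 24 MRI is lost in every such case; the documents make that likely, not certain. It does not remove the problem, because a site that follows 9.2.2 as written has permission to skip what 4.4 says must be done.

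Two further inferences are tempting and not supported:

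- *Safety follow-up ends for these women.* It does not. Protocol 4.4.1 still asks for clinical and laboratory follow-up after withdrawal, and Protocol 9.4.1.6 has adverse events monitored until they resolve, stabilise or are explained, or until the patient is lost to follow-up or dies.
- *The loss differs by arm because unblinding follows adverse events.* That pathway is the deliberate emergency code break. The withdrawal sentence covers inadvertent disclosure only, and nothing in the documents links that to adverse events or to one arm.

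It is also fair to say that the benefit to the primary analysis is limited. PP requires completion of treatment, compliance within 80% to 120% and no deviation that could affect the primary outcome, so an MRI taken at early withdrawal would not by itself put her in PP. The gain is mainly in the supportive mITT analysis.

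**Conclusion.** The point holds as a minor one. The unblinding rule in both documents conflicts with the rule on end-of-treatment assessments and with the follow-up asked for in Protocol 4.4.1, and no order of precedence is given. Following the unblinding rule as written is likely to remove the affected woman from both efficacy sets, with no recovery through imputation.

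The number affected is unknown and may be very small or zero; each case would be about 3% to 4% of an arm under the assumptions shown. The conclusion assumes that Week 24 is the only scheduled post-baseline MRI-PDFF. That is what the readable text lists; the full schedule tables are not visible in the public copies. It also assumes that disclosure occurs before the Week 24 visit and that no MRI is taken at withdrawal. The documents do not say whether a participant stays in the trial after a deliberate code break, so nothing is concluded about that case.

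**What to change.** Reconcile Protocol 9.2.2 and SAP 7.5 with the protocol summary, Protocol 4.4, 4.4.1 and 7.2, and SAP 7.2, along these lines:

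- Inadvertent unblinding is recorded as a protocol deviation and does not excuse outcome collection.
- The end-of-treatment MRI and the other end-of-treatment assessments are still sought.
- The participant is kept in mITT once her MRI is obtained; PP membership follows the existing PP criteria.
- A sensitivity analysis may leave her out.

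If follow-up has already finished, the SAP can still state, before database lock, that any such withdrawals will be reported by arm, reason and analysis set.

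The cost is one sentence in each document and one small extra analysis; the assessments are already scheduled. Whether study drug continues after inadvertent unblinding is a separate matter and is not addressed here.
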